1. BACKGROUND AND DESIGN

The main characteristics of this trial are summarised in the latest TAPPS trial protocol. Please refer to this for full details.

1.1 Trial summary

Malignant pleural effusions (MPE) are a major cause of morbidity amongst cancer patients, usually leading to significant breathlessness. Currently, there are about 250,000 new cases per year in the United States and the UK, which causes a heavy burden on healthcare services.[1] Median survival from diagnosis is typically only around 4-6 months.[2]

Management of malignant pleural effusions usually entails attempting pleurodesis. The most proven and widely-used sclerosant is sterile talc, which may be given using one of two methods. The first, more traditional approach is to remove the fluid using a bedside intercostal chest drain and to then instil talc slurry through it. An alternative is to perform a local anaesthetic (medical) thoracoscopy and to spray a powder ('poudrage') under direct vision of the pleural surfaces.

Thoracoscopy is becoming more widely available in the UK and is used frequently to perform talc poudrage. Our own audit data has suggested a benefit to using this approach over bedside talc slurry, although the published trials in this area have been few and have suffered from methodological flaws.[3] There are also potential benefits in patients' quality of life, and costs to healthcare providers in using poudrage, as this procedure usually involves a shorter hospital stay.

The TAPPS trial aims to answer definitively whether there are significant differences in efficacy, safety and cost in using thoracoscopy and talc poudrage over talc slurry pleurodesis for the management of malignant pleural effusions. We aim to recruit 330 patients from across the UK and randomise them to receive either talc poudrage (intervention) or bedside talc slurry (control), and to then compare pleurodesis success rates at three months. This trial has the potential to inform and change current NHS and international practice by determining the most effective approach to managing this difficult group of patients.

1.2 Patient eligibility criteria

1.2.1 Inclusion criteria

- 1. Clinically confident diagnosis of malignant pleural effusion requiring pleurodesis, defined as:
 - a) Pleural effusion with histocytologically proven pleural malignancy, **OR**
 - b) Pleural effusion in the context of histocytologically proven malignancy elsewhere, without a clear alternative cause for fluid, OR
 - c) Pleural effusion with typical features of malignancy with pleural involvement on cross-sectional imaging (CT/MRI), without a clear alternative cause for fluid.
- 2. Fit enough to undergo local anaesthetic thoracoscopy
- 3. Expected survival >3 months
- 4. Written, informed consent to trial participation

1.2.2 Exclusion criteria

- 1. Patients in whom thoracoscopy is the only reasonable approach to making a diagnosis, and in whom such a diagnosis would significantly influence further management.
- 2. Age < 18 years
- 3. Females who are pregnant or lactating
- 4. Evidence of extensive lung entrapment on CXR or CT, or significant fluid loculation on ultrasound scan, to a level which would normally be a contraindication to attempted talc pleurodesis
- 5. Insufficient volume or position of pleural fluid on lateral decubitus thoracic ultrasound to safely perform local anaesthetic thoracoscopy without further intervention being necessary
- 6. Previously documented adverse reaction to talc
- 7. Clear contraindication to thoracoscopy or chest tube insertion

1.3 Trial intervention

Patients will be randomised, in a 1:1 ratio using minimisation with a random element, to undergo either chest drain insertion with talc slurry pleurodesis or thoracoscopy with talc poudrage. Randomisation will be performed using a central telephone service and will take place following consent. The allocated trial intervention will take place within 72 hours of the allocation being determined.

Due to the inherent and substantial differences between the two methods being tested, this trial cannot be performed ethically or safely in a blinded manner using dummy or sham procedures. The trial will therefore be undertaken in an open-label manner, such that both the trial participant and the research team are aware of the allocated intervention.

1.4 Bias reduction

Due to the open-label nature of this trial, the potential for introducing bias into data collection and analysis is inherently greater than if the trial were performed in a fully blind fashion, especially given that it will typically be the local trial research teams who are also responsible for the clinical management of participants. Therefore, in order to minimise the possibility of bias in the primary outcome, the decision to undertake further pleural intervention in patients who develop breathlessness and have a small-volume recurrent effusion will be discussed with a blinded assessor.

1.5 Changes from v1.0 of the Statistical Analysis Plan

- Changed method of analysis for pleurodesis failure from competing risk time-to-event model to logistic regression model (as was specified in the protocol)
- Removed secondary outcome 'Requirement for further pleural procedures up to 180 days post randomisation, based on an independent, blinded assessment'. This was because:
 - Blinded assessment and corroboration of the need for pleural intervention were already required for any case which is likely to be contentious, as per section 1.4 above.
 - Without clinical contact, the information upon which the assessment would be made was felt to be insufficient to determine whether a further pleural procedure would have been necessary, and thus the clinical relevance of the outcome was felt to be doubtful
 - It is likely that this assessment would rely primarily on the patient's x-ray appearance, which is being addressed as another secondary outcome.
- Restricted subgroup analyses to only the primary outcome
- Updated Stata command for analysing chest x-ray pleural opacification, EQ-5D, SF36, thoracic pain, and breathlessness, from *xtmixed* to *mixed* (the command *mixed* replaced *xtmixed* in more recent versions of Stata)

- Removed sensitivity analysis for primary outcome based on measure pleurodesis failure from date of procedure rather than date of randomisation.
- Removed the subgroup analysis for use of NSAIDs at baseline as this question has now been addressed in the TIME1 trial
- Removed the subgroup analysis for previous radiotherapy at baseline
- Added additional exploratory outcomes
- Specified that adverse events and serious adverse events would be summarised and analysed within 7 days of randomisation (in addition to within 30 and 180 days)

All changes to the Statistical Analysis Plan were made before database lock.

2. OUTCOME MEASURES

2.1 Primary outcome measure

2.1.1 Primary outcome measure description

The primary endpoint is the number of patients who experience pleurodesis failure up to three months (90 days) post randomisation. The overall survival rate from diagnosis of malignant pleural effusion is generally only a few months. For this reason, the primary endpoint being measured at three months is likely to be a more clinically relevant period over which pleurodesis failure will impact on patient care and quality of life. The proportion of patients experiencing pleurodesis failure by 1 and 6 months (30 days and 180 days) will be secondary outcomes.

A patient is defined as experiencing pleurodesis failure if they undergo any of the following procedures on the side ipsilateral to their trial intervention:

- Therapeutic pleural aspiration of ≥100mls, or
- Insertion of an intercostal drain for fluid drainage, or
- Insertion of an indwelling pleural catheter, or
- Medical or surgical thoracoscopy

A patient is also deemed to have failed pleurodesis if their primary physician decides that they require one of the above pleural interventions, but the intervention is not performed (e.g. in the event of death or patient choice against procedure). A patient who does not meet the criteria for a pleurodesis failure will be deemed as having had a successful pleurodesis.

The primary physician is not blind to treatment arm, however all decisions to intervene or not in effusions which occupy less than or equal to one third of the hemithorax should be discussed with a second clinician who is to remain blind to treatment allocation.

2.2 Secondary outcome measures

2.2.1 Secondary outcome measures description

- The number of patients with pleurodesis failure up to 30 days post randomisation.
- The number of patients with pleurodesis failure up to 180 days post randomisation.
- Percentage radiographic (chest x-ray) pleural opacification at the 1-month, 3-month and 6month post randomisation follow-up visits, and after initial drain removal.
- Self-reported health-related quality of life at the 1-month, 3-month and 6-month follow-up post-randomisation visits, as measured using the SF-36 and EQ-5D questionnaires.
- Self-reported thoracic pain and breathlessness at 7, 30, 90 and 180 days post randomisation, measured using visual-analogue scale (VAS) scores.
- All-cause mortality up to 180 days post randomisation
- Time to pleurodesis failure, censored at 180 days post randomisation.
- Number of nights spent as a hospital inpatient up to 90 days post randomisation, including length of initial stay

2.2.2 Clarification of secondary endpoints

Percentage chest x-ray opacification

Percentage chest x-ray opacification will be assessed by two independent clinicians, at least one of whom is a radiologist. Both will be blind to treatment allocation. They will be asked to provide a measurement of percentage hemithorax opacification due to pleural effusion using an established

method.[4] Briefly, using appropriate radiological software, separate polygons are drawn by hand around both the hemithorax the pleural effusion. The size of the effusion is given as the ratio of the area of one polygon to the other. Both assessors will be asked to agree rescored values if there is a discrepancy of more than 15% between their two original measurements. The final value will be calculated from the mean of the two assessors' measurements.

Assessments of effusion size will only be made up to the point when a patient undergoes any intervention for fluid management on the side of the trial procedure.

2.3 Exploratory outcomes (added during the trial)

- Categorical version of percentage radiographic (chest x-ray) pleural opacification at the 1month, 3-month and 6-month post randomisation follow-up visits, and after initial drain removal, with categories as:
 - 1. No fluid visible
 - 2. 1-24% opacification due to fluid (small effusion)
 - 3. 25-49% due opacification due to fluid (moderate effusion)
 - 4. 50% or greater opacification due to fluid (large effusion)
- Degree of visible lung entrapment on chest x-ray at 6 months post-randomisation. Categories are:
 - 1. No lung entrapment
 - 2. Minor lung entrapment (1-24% unexpanded lung)
 - 3. Moderate lung entrapment (25-49% unexpanded lung)
 - 4. Severe lung entrapment (50% or greater unexpanded lung)

Assessment of lung entrapment will be made by the same clinicians assessing pleural opacification.

3. SAMPLE SIZE

Previous literature and our own audit data suggest that patients with a WHO performance status score of 2 or better have approximate pleurodesis failure rates of 10% with a thoracoscopy, and 30% with standard chest tube and talc slurry pleurodesis.[5]

In order to detect a 15% difference in pleurodesis failure at 3 months (10% thoracoscopy and poudrage vs. 25% chest drain and talc slurry) with 90% power, a 5% significance level, and 10% loss to follow-up, we would require 325 patients. This has been rounded up to 330 patients (165 patients in each treatment arm).

4. DATA CAPTURE AND MANAGEMENT

4.1 CRF descriptions and collection schedule

CRF	Frequency of	CRF description	Usual time of CRF
	collection		completion
Enrolment	Once	Collection of baseline	Immediately after
		characteristics	consent
Randomisation	Once	Inclusion/Exclusion	Immediately after
		criteria and	enrolment
		minimisation	
		information.	
Chest drain	Once. Only one form	Collection of data	Immediately after
insertion /	to be completed.	relating to treatment	procedure performed
Thoracoscopy		arm procedure	
and poudrage			
Discharge	Once	Collection of data	Around time of
		relating to inpatient	discharge
		period and post-	
		procedure	
		complications	
Follow-up	At each follow-up visit	Collection of data	Months 1, 3 and 6 post
		relating to pleurodesis	randomisation
		failure and other	
		follow-up information	
Health service	At each follow-up visit	Collection of health	Months 1, 3 and 6 post
use		economic data relating	randomisation
questionnaire		to post discharge	
		period	

4.2 Trial data management

4.2.1 Day to day data management

A trial database will be established by the Oxford Respiratory Trials Unit using the OpenClinica system. Data will be collected on the above CRFs and sent to the database manager, who will assume responsibility for data entry and data management until the database is locked. CRF data of all randomised patients will be entered onto the database using a single data entry process. All transcribed CRFs will be checked for inconsistent, ambiguous or missing information. The presence of any of these will lead to the generation of a data query. Data queries will be dealt with by the trial manager and database manager. The trial database will be amended on receipt of a response to a data query.

4.2.2 At time of analysis

On a date agreed by the Trial Steering Committee and the Trial statistician, the database manager will generate a trial dataset from the OpenClinica database. This will act as the frozen dataset. If further data queries are then raised by the trial statistician then the database may be changed based upon the responses to the queries. This will be done under the oversight of the trial statistician and the trial manager. After this, the database will be locked.

5. ANALYSIS PRINCIPLES

5.1 General principles for analysis

The primary analysis for each outcome will be by intention-to-treat, meaning that all patients on whom an outcome is available will be included in the analysis, and will be analysed according to the treatment group to which they were randomised. More information on which patients are considered to have an available outcome is available in later sections. All tests will be two-sided, and will be considered statistically significant at the 5% level.

For each analysis, the following summaries will be provided:

- The number of patients in each treatment group who are included in the analysis
- The mean (SD) or median (IQR) in each treatment group for continuous outcomes, or the number (%) of patients experiencing an event for binary or time-to-event outcomes (time-to-event outcomes will also present the median time to event in each treatment arm if applicable)
- The treatment effect (difference in means for continuous outcomes, odds ratio for binary outcomes, hazard ratio for time-to-event outcomes, rate ratio for count outcomes) with its 95% confidence interval and a p-value

All analyses will adjust for the minimisation variables (type of underlying malignant disease [mesothelioma, lung cancer, breast cancer, other] and WHO performance status [0-1 or 2-3]).[6-8] Minimisation variables will be included as covariates in the regression model for each outcome.

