5.7 Sensitivity analyses

5.7.1 Missing data

Sensitivity to missing data for the primary outcome will be assessed under a range of missing-not-atrandom scenarios. This will be performed using the following formula:

$$\Delta = \Delta_{\rm CC} + Y_1 P_1 - Y_2 P_2$$

where Δ is the treatment effect under the missing-not-at-random scenario, Δ_{CC} is the treatment effect under a complete case scenario (i.e. where patients with a missing outcome are excluded), P₁ and P₂ are the proportion of patients who were excluded in groups 1 and 2 respectively, and Y₁ and Y₂ are the proportion of patients in treatment group 1 and 2 with missing data who are assumed to experience an event (i.e. who experience the primary outcome). For this sensitivity analysis, we will consider all patients who were excluded from the primary analysis due to missing data. We assume that the standard error for Δ is approximately equal to the standard error for Δ_{CC} .

 Y_2 will be varied between 10%, 25%, 50%, 75%, and 90% and for each value of Y_2 , Y_1 will be varied between Y_2 -10%, Y_2 , and Y_2 +10%. For example, for Y_2 =25%, Y_1 will vary between 15%, 25%, and 35%.

For each scenario, a treatment effect and 95% confidence interval will be calculated, which will be compared with results from the main analysis of the primary outcome to see if conclusions are affected by different assumptions regarding the missing data.

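### The missing-data sensitivity analysis in SAP 5.7.1 needs a risk difference and its standard error, but SAP 5.1 plans an interval only for the odds ratio

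*SAP*

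**What the plan says.** - **Effect measure.** SAP 5.1 lists what every analysis will present. For binary outcomes this is the number (%) with an event in each arm and a treatment effect with 95% CI and p-value, the effect being the "odds ratio for binary outcomes". SAP 5.3 obtains it for 90-day pleurodesis failure from a logistic model adjusted for the minimisation variables, in patients with outcome data. Table 3 (SAP 6.4.3) has one treatment-effect column and names no scale.
- **Sensitivity analysis.** SAP 5.7.1 computes Δ = Δ_CC + Y₁P₁ − Y₂P₂. Δ_CC is the complete-case treatment effect, P is the proportion excluded in each arm, and Y is the assumed proportion with the event among those excluded. The standard error of Δ_CC is carried over to Δ. Each scenario yields an effect and a 95% CI, "which will be compared with results from the main analysis of the primary outcome".
- **Design target.** SAP 3 sizes the trial on the absolute scale: "In order to detect a 15% difference in pleurodesis failure at 3 months (10% thoracoscopy and poudrage vs. 25% chest drain and talc slurry").

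**The concern.** Y₁P₁ and Y₂P₂ are proportions of patients. They can be added to a difference in proportions, but not to an odds ratio or its logarithm. The only treatment effect and standard error that the SAP plans for this outcome come from a logistic model and are reported as an odds ratio.

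An analyst who follows the text literally would mix scales. One who sees the problem must choose, after the data are in, whether Δ_CC is crude or adjusted, which standard error goes with it, and what it is compared with.

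At stake is the one prespecified check on whether missing outcomes could change the primary conclusion. An adjusted risk difference would also give an interval on the scale of the 15-point target, but that is a secondary benefit.

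**Working it through.** **Inputs.** Failure 10% (poudrage) and 25% (slurry), 90% power, 5% level, 10% loss, 325 rounded to 330: SAP 3. Two-sided tests: SAP 5.1. 1:1 allocation: SAP 1.3. Grid for Y₁ and Y₂: SAP 5.7.1. Two assumptions are added: P₁ = P₂ = 10%, taken from the planned loss to follow-up, and group 1 = poudrage, because 5.7.1 does not label the groups.

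**1. The plan's own figure.** Two-proportion formula, mean rate 0.175:

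n = [1.960·√(2·0.175·0.825) + 1.282·√(0.10·0.90 + 0.25·0.75)]² / 0.15² = 132.8 per arm.

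With continuity correction: (132.8/4)·[1 + √(1 + 4/(132.8·0.15))]² = 145.8, so 146 per arm and 292 in total. 292/0.90 = 324.4, so 325. This matches SAP 3.

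**2. Does the logistic analysis harm power?** The design rates give an odds ratio of (0.10/0.90)/(0.25/0.75) = 0.333. With 148.5 evaluable per arm (165 × 0.90), the standard error of the log odds ratio is √[(1/0.09 + 1/0.1875)/148.5] = 0.333. Power is Φ(1.099/0.333 − 1.960) = 91%. Power is not the problem.

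**3. Section 5.7.1 applied to the planned effect.** Take Y₁ = 60%, Y₂ = 50%. The added term is 0.6·0.1 − 0.5·0.1 = +0.010.

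- Added to the odds ratio: 0.333 + 0.010 = 0.343.
- Added to the log odds ratio: exp(−1.099 + 0.010) = 0.337.
- Implied by the assumptions: poudrage 0.9·0.10 + 0.1·0.60 = 0.150; slurry 0.9·0.25 + 0.1·0.50 = 0.275; odds ratio (0.150/0.850)/(0.275/0.725) = 0.465.

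Over the full grid:

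| Reading of the formula | Lowest | Highest |
|---|---|---|
| Term added to odds ratio | 0.323 | 0.343 |
| Term added to log odds ratio | 0.330 | 0.337 |
| Odds ratio implied by the same assumptions | 0.322 | 0.510 |

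Range over P for the example with Y₁ = 60%, Y₂ = 50%:

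- P = 5%: formula 0.338; implied (0.125/0.875)/(0.2625/0.7375) = 0.401.
- P = 20%: formula 0.353; implied (0.200/0.800)/(0.300/0.700) = 0.583.

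Reversing the labels (group 1 = slurry, Y₁ = 60%, Y₂ = 50%) gives 3.00 + 0.01 = 3.01, against an implied (0.285/0.715)/(0.140/0.860) = 2.45. The mismatch does not depend on the labelling.

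**4. Standard error.** At the design rates with 148.5 per arm, the standard error of the risk difference is √[(0.09 + 0.1875)/148.5] = 0.0432. That of the log odds ratio is 0.333. One cannot stand in for the other.

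**5. Is a risk difference enough?** No. If Y is the event proportion among missing patients, the arm rate is (1 − P)p + PY, so

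Δ = (1 − P₁)p₁ − (1 − P₂)p₂ + Y₁P₁ − Y₂P₂.

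The SAP formula keeps p₁ − p₂ unweighted. With P₁ = P₂ = 10% and Y₁ = Y₂ it returns −15.0 points; the weighted value is 0.9 × (−15.0) = −13.5. With equal P the error is P × 15 points: 0.75 at 5%, 1.5 at 10%, 3.0 at 20%.

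The formula would be exact if Y were the missing-minus-observed difference d in event rate, since (1 − P)p + P(p + d) = p + Pd. The present grid does not fit that reading: 90% added to a 25% slurry rate would be 115%.

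**The case against.** **The formula shows that a risk difference is meant.** This is fair as to intent, and 5.7.1 never says that Δ is an odds ratio. But the SAP then leaves open whether Δ_CC is crude or adjusted and where its standard error comes from, and the promised comparison is still with a main result on another scale. That part of the point stands.

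**A reader might infer that the absolute effect is hidden.** The SAP does not support this. Section 5.1 and Table 3 put number (%) per arm beside the odds ratio, so anyone can subtract and build a crude interval. For illustration, 37/148 against 15/148 gives 14.9 points (6.4 to 23.4). The arm percentages also remove the ambiguity of an odds ratio quoted without a base rate, and the 10% and 25% in SAP 3 let the target be restated as an odds ratio of 3.0 (slurry against poudrage). Only the adjusted difference and its interval are missing.

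**A reader might infer that sizing on a difference and testing by logistic regression is an error.** It is not. The null hypothesis is the same, 325 reproduces, and power on the log-odds scale is 91%.

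**A reader might infer that adding a risk difference repairs 5.7.1.** It does not, because of the missing weights shown in step 5.

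**The effect may be small in practice.** True if few outcomes are missing: every discrepancy above shrinks with P.

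**Conclusion.** The point holds as an inconsistency between SAP 5.1/5.3 and SAP 5.7.1. As written, the sole missing-data sensitivity analysis of the primary outcome lacks a planned estimate, standard error and comparator on the scale its formula requires. At the design rates with 10% missing per arm, literal use on the odds ratio would show movement only from 0.323 to 0.343, while the stated scenarios imply 0.322 to 0.510. The result would look almost insensitive to missing data when it is not. Even on the right scale, the formula is off by 1.5 points under those assumptions when Y₁ = Y₂.

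These sizes rest on the design rates, on equal missingness at the planned loss, and on unadjusted calculations. The scale mismatch itself depends on none of them. The primary test, sample size and power are sound. This is a modest correction and no threat to the main analysis.

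**What to change.** 1. **SAP 5.1 and 5.3:** beside the odds ratio, report the adjusted risk difference with 95% CI for 90-day pleurodesis failure, by marginal standardisation from the same logistic model. Doing so at 30 and 180 days is optional. Add a column to Table 3 and name the scale in each.
2. **SAP 5.7.1, scale:** define Δ_CC and its standard error as that adjusted risk difference, state which arm is group 1, and compare every scenario with the adjusted risk difference.
3. **SAP 5.7.1, formula:** either weight the observed arm rates by (1 − P₁) and (1 − P₂) before adding Y₁P₁ and Y₂P₂, which keeps the present grid, or redefine Y as the difference in event rate between missing and observed patients and re-express the grid accordingly.

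Cost: one post-estimation command, one table column and a revised formula. The sample size and primary test stay as they are.
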